7.2 Study Conduct

7.2.1 Accrual Patterns

Tables summarizing accrual by site number, overall and by treatment group will be generated.

7.2.2 Protocol Violations

A relevant protocol deviation is defined as a deviation from the protocol which is programmed in the database and which could potentially affect the interpretability of the study results.

The number and percentage of subjects with any relevant protocol deviation and each specific deviation will be presented overall and by treatment group.

The following eligibility deviations are considered relevant in this study and will be summarized for all randomized subjects:

1. Any prior systemic anti-myeloma therapy
2. Non-measurable disease. This occurs when none of the following three conditions are met:
 1. IgG, IgA, or IgM M-protein ≥ 0.5 g/dL

2. M-protein ≥ 200 mg in 24-hour urine.
3. Serum free light chain (sFLC) assay showing involved FLC level ≥ 10 mg/dL (≥ 100 mg/l) provided the serum FLC ratio is abnormal
3. No baseline tumor assessment. This occurs when there are no tumor assessments at all (laboratory assessments) on or prior to first day of dosing. See [section 4.1.2.1](#), for definition of adequate tumor assessment.

Also, the following on-treatment deviations are considered relevant in this study and will be summarized for all treated subjects:

4. Non-protocol specified systemic anti-myeloma therapy prior to discontinuation of study therapy
5. Received non-assigned treatment regimen throughout the study.
6. Subjects continuing to receive study therapy after 10 weeks of first documented progression per investigator (as progression should be confirmed).

If assessments based on the central laboratory is unavailable, but the local laboratory results are available, then those will be used for evaluating deviations 2 and 3.

A by subject listing of relevant protocol deviations will be provided.

7.3 Study Population

7.3.1 Subject Disposition

A frequency table of enrolled subjects, broken down by whether or not they were randomized, and the reasons for not being randomized, will be produced.

Subject disposition during the treatment period will be summarized, overall and by treatment group. The number and percentage of subjects randomized, treated, still on treatment and discontinued from the treatment will be presented.

By-subject listings will also be produced to accompany the tables on enrollment and the subject disposition table.

In addition, a by-subject listing indicating whether the subject was included in each of the analysis populations will be provided.

7.3.2 Demographic and Subject Characteristics

Demographic and baseline characteristics will be summarized, overall and by treatment group. The following parameters will be summarized; age at the time of informed consent (years), age category at time of informed consent (<65 years, ≥ 65 years), and (<75 years, ≥ 75 years), gender (Male, Female), weight (kg) and ECOG performance status (0,1,2) .

An accompanying by-subject listing of demographic and subject characteristics will be presented.

7.3.3 Disease Characteristics at Baseline

Baseline disease characteristics will be summarized, overall and by treatment group. The following parameters will be presented to summarize baseline disease:

- Serum M-protein (g/dL)
- Urine M-protein (mg/24 hours)
- Myeloma type (IgG, IgA, IgM, Light chain disease)
- Number of lytic bone lesions (0, 1-3, >3)
- Myeloma¹⁸ Risk Categories
 - ◆ High risk: ISS stage II or III **and** t(4;14) or del(17p) abnormality
 - ◆ Low risk: ISS stage I or II **and** absence of t(4;14), del(17p) and 1q21 abnormalities and age < 55 years
 - ◆ Standard risk: any subjects not meeting the definition of high or low risk.
 - ◆ Not Evaluable: Subjects having missing data preventing the classification in the other 3 categories
- Individual FISH/Cytogenetic abnormalities (del 17p, 1 q21 amplification, t(14; 16), t(4; 14), del 13, 1p32.3, 1q21, t(14;20), hypodiploidy)
- β 2 microglobulin (mg/L) (<3.5, \geq 3.5-<5.5, \geq 5.5)
- Albumin (g/L) (<3.5, \geq 3.5)
- LDH (<300 IU/L, \geq 300 IU/L)
- Creatinine Clearance (mL/sec) (<0.5, 0.5 -<1, 1-<1.5, \geq 1.5)
- Soft tissue plasmacytomas (Yes, No)
- ISS Stage at randomization (I, II, III)
- Time from disease diagnosis to randomization (months)

An accompanying by-subject listing of disease characteristics at baseline will be presented.

7.3.4 General Medical History

The number and percentage of subjects with any relevant medical history and by body system will be presented, overall and by treatment group.

By subject listings of medical history will be provided. A by subject listing of pregnancy test data will also be provided.

7.3.5 Baseline Safety Laboratory Tests

Baseline safety laboratory evaluations will be the last available samples taken on or before Cycle 1, Day 1 and within 60 days before randomization.

Baseline safety laboratory values will be presented by CTC severity grade, by treatment group. Separate tables will be generated for hematology (hemoglobin, WBC, ANC [neutrophils plus bands], ALC [absolute lymphocyte count] and platelets), liver function (ALT, AST, alkaline phosphatase, albumin, and total bilirubin) and renal function/electrolytes (sodium, potassium, bicarbonate, chloride, calcium, glucose, and creatinine, creatinine clearance < 60 ml/min, ≥ 60 ml/min). Sodium, potassium, chloride, calcium, and glucose will be presented separately, based on their high and low values.

7.4 Extent of Exposure

7.4.1 Study Therapy

Lenalidomide, oral dexamethasone and IV dexamethasone are given at fixed doses and are not adjusted for body surface area or weight. The elotuzumab dose, in contrast, is adjusted for weight. Throughout this SAP, a subject's elotuzumab dose level at a particular time point will refer to the actual dose, in mg/kg, rather than their planned dose. A subject's actual elotuzumab dose level will be computed by dividing their total dose delivered, in mg, as recorded on the "Record of Study Medication" eCRF page, by their latest pre-dose weight, in kg, on Day 1 of that cycle.

7.4.1.1 Duration of Study Therapy

The number of cycles of treatment received by subjects will be summarized (using n, mean, STD, median, min, max, q1 and q3) by treatment group. A summary of the number of subjects taking each drug in each cycle will also be presented by treatment group.

The duration of each treatment (elotuzumab, dexamethasone [oral, IV, and oral and IV combined] and lenalidomide), in months, will be calculated as:

$$(date\ of\ last\ dose\ of\ the\ drug - date\ of\ first\ dose\ of\ the\ drug + 1) / 30.4375$$

Duration of each of the study treatments will be summarized by treatment group.

7.4.1.2 Dose Modifications

Elotuzumab

- **Dose Reduction**

Reduction of Elotuzumab dosing is not permitted as per the protocol.

- **Dose Delay**

A delay for Elotuzumab will be computed based on records from the dosing CRF page. A delay in Elotuzumab dosing will be defined as the number of days from the start date of the previous infusion to the start date of the current infusion being > 8 days and ≤ 10 days (if in cycles 1, 2 or first infusion of cycle 3) or > 15 days and ≤ 21 days (from cycle 3, second infusion of cycle 3 - cycle 19) or > 29 days and ≤ 35 days (from cycle 20 onwards).

For courses with a delay of Elotuzumab infusion, the time of delay in infusion will be summarized in the categories: 2- 3 days, 4 - 7 days.

The number and percentage of subjects with any dose delay, with 1, 2, 3, or ≥ 4 reported delays will be summarized. For subjects with a delay, their reason for delay (from the dose change page of the CRF) will be summarized in the groups: “hematologic toxicity”, “non-hematologic toxicity”, “AE”, “dosing error” and “other”. For subjects without an available reason for delay, the category “unknown” will be used.

A by-subject listing for dose delay will be presented for all treated subjects. This listing will include all reported delays per CRF, regardless of whether the subject had a computed delay based on the actual dosing dates.

- **Dose Omission**

An omission for Elotuzumab will be calculated based on records from the study medication CRF page. If the interval between the two dosing dates for Elotuzumab is >10 days (in cycles 1, 2 or first infusion of cycle 3) or >21 days (from the second infusion of cycles 3-18), or > 35 days from cycle 19 and beyond, the dose will be considered to have been omitted.

For courses with an omission of Elotuzumab infusion, the time between the previous and current infusion will be summarized in the categories: 11 - 14, 15 - 21, 22 - 27, 28 - 35, ≥ 36 days.

The number and percentage of subjects with a dose omission, and with 1, 2, 3, or ≥ 4 omissions will be summarized. For subjects with an omission, their reason for omission (from the dose modification page of the CRF) will be summarized in the groups: “hematologic toxicity”, “non-hematologic toxicity”, “AE”, “dosing error” and “other”. For subjects without an available reason for omission, the category “unknown” will be used.

A by-subject listing for dose omission will be presented for all treated subjects. This listing will include all reported omissions per CRF, regardless of whether the subject had a computed omission based on the actual dosing dates.

- **Dose Interruption**

The number and percentage of subjects with any interruption in their elotuzumab infusion, with 1, 2, 3, or ≥ 4 interruptions, with an interruption due to “infusion reaction”, “infusion administration issues” and “other” will be presented. In addition, duration of interruptions (in minutes) will be summarized via descriptive statistics.

A by subject listing will be generated for elotuzumab IV interruptions. This listing will include reason for interruption, whether the infusion was resumed, and duration of the interruption.

- **IV Rate Reduction**

The number and percentage of subjects with any elotuzumab IV rate reduction, with 1, 2, 3, or ≥ 4 rate reductions, and with rate reductions due to “infusion reaction,” “infusion administration issues,” and “other” will be presented.

A by subject listing will be generated for elotuzumab IV rate reductions.

Lenalidomide

- **Dose Reduction**

Reduction of Lenalidomide will be computed based on the actual dose received. In any study day (excluding, cycle 1, day 1), the drug will have a calculated reduction compared to the previous day, if the actual level of the administered dose is below the actual level of the administered dose in the previous instance. The information for this analysis will be derived programmatically, using the total daily dose on the “Record of Study Medication - lenalidomide” eCRF page.

The daily dose levels are defined as follows:

Dose level 0 or full dose (25 mg): ≥ 20.0

Dose level -1 (15 mg): 12.5 mg to < 20.0

Dose level -2 or starting dose for moderate renal impairment (10 mg): 8.75 to < 12.5 mg

Dose level -3 for subjects with severe renal impairment (15 mg every 48 hours): 6.25 to < 8.75 mg

Dose level -4 for subjects with End Stage Renal Disease (ESRD) (5 mg): < 6.25 mg

The number and percentage of subjects with a dose reduction, and the lowest dose level achieved per subject (-1, -2, -3, \leq -4), will be presented by treatment group. This table will be broken out by whether the subject started at the standard dose level or at the 10 mg dose level.

The reason for dose reduction as reported by the investigator will be tabulated for all instances with a calculated reduction based on the dose modification for Lenalidomide page. A category “unknown” will be defined for all calculated reductions with no reason reported by the investigator.

A by-subject listing of dose reductions will be generated. This will include all reported reductions per investigator, regardless of whether it met the requirements for a calculated reduction.

- **Dose Interruption**

In any cycle, the Lenalidomide dose will be considered as interrupted if there is a gap of two or more days between two dosing dates within that cycle where the subject did not receive the study drug. This will be calculated based on the information from the dose modification CRF for Lenalidomide.

The number and percentage of subjects with dose interruption, with 1, 2, 3, or ≥ 4 reported interruptions will be presented. For subjects with a computed interruption, their reason for

interruption will be summarized from the dose modification CRF. For subjects without an available reason for interruption, the category “unknown” will be used.

Dexamethasone (IV) and Oral

For IV dexamethasone the following summaries will be provided:

- The number of subjects with any dose delay, with 1, 2, 3, or ≥ 4 reported delays, and with a reason for delay of “hematologic toxicity”, “non-hematologic toxicity”, “AE”, “dosing error” and “other”.
- The number of subjects with any reported dose omission, with 1, 2, 3, or ≥ 4 reported omissions, and with a reported reason for omission of “hematologic toxicity”, “non-hematologic toxicity”, “AE”, “dosing error” and “other”.
- The number of subjects with any reduction in the dose of the drug, and with a reason for the reduction of “hematologic toxicity”, “non-hematologic toxicity”, “AE”, “dosing error”, and “other”).

For PO dexamethasone the following summaries will be produced:

- The number of subjects with any dose modification, with 1, 2, 3, or ≥ 4 reported modifications, and with a reason for the modification of “hematologic toxicity”, “non-hematologic toxicity”, “AE”, “dosing error” and “other”).

By subject listings of record of study medication for each of IV dexamethasone and PO dexamethasone will be provided.

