4.5 Selection and Timing of Dose for Each Subject

4.5.1 Study Drug Administration

Dexamethasone

On weeks without elotuzumab (including the control arm), administer the weekly dose of 40 mg dexamethasone on Day 1, 8, 15, and 22 (-1 to +3 days). At the investigator's discretion, the oral dexamethasone may be given as a split dose over 2 consecutive days each week.

On weeks of elotuzumab infusion, administer dexamethasone as a split dose of:

- 28 mg po (between 3 - 24 hours prior to the start of elotuzumab infusion) AND
- 8 mg IV (on the day of elotuzumab infusion at least 45 min prior to the start of infusion).
- At the discretion of the investigator, the oral dexamethasone component may be given as a split dose 12 - 24 and 3 hours prior to elotuzumab.

Elotuzumab

Elotuzumab will be administered intravenously at a dose of 10 mg/kg weekly (Days 1, 8, 15, and 22 of a 4-week cycle) of the first 2 cycles and every 2 weeks (Day 1 and Day 15) for Cycles 3 through 18, then at a dose of 20 mg/kg every 4 weeks Cycle 19 (Day 1) and beyond. A window of -1 to +3 days is permitted in Cycles 1 and 2.

In Cycle 1 and 2, an elotuzumab dose that falls outside of the pre-specified window must be skipped.

In Cycles 3 and beyond, elotuzumab dosing may be delayed for up to 1 week as clinically indicated. The reason for the delay must be recorded on the CRF. If unable to administer within 1 week, then the dose should be skipped and resumption of the elotuzumab continues per the protocol defined schedule.

In addition, the following must also be administered 30 - 90 min prior to any elotuzumab:

- H1 blocker: diphenhydramine (25 - 50 mg po or IV) or equivalent
- H2 blocker: ranitidine (50 mg IV) or equivalent
- Acetaminophen (300 - 1000 mg po).

See [Appendix 3](#) for elotuzumab dosing instructions.

Lenalidomide

Lenalidomide will be taken orally 25 mg once daily for the first 3 weeks of a 4-week cycle. On the days of elotuzumab administration, the dose of lenalidomide is to be administered at least 2 hours after completion of elotuzumab dosing. Subjects should not break, chew or open the capsules.

Table 4.5.1-1: Treatment Schedule

Investigational Arm (ELd Arm)												
Cycle #	1 - 2				3 - 18				19 +			
Day # (-1/+3 days)^a	1	8	15	22	1	8	15	22	1	8	15	22
Dexamethasone - PO	28 mg	28 mg	28 mg	28 mg	28 mg	40 mg	28 mg	40 mg	28mg	40 mg	40 mg	40 mg
Dexamethasone - IV	8 mg	8 mg	8 mg	8 mg	8 mg	-	8 mg	-	8 mg	-	-	-

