Elotuzumab - IV	10 mg/kg	10 mg/kg	10 mg/kg	10 mg/kg	10 mg/kg	-	10 mg/kg	-	20 mg/kg	-	-	-
Lenalidomide - PO	25 mg Days 1 - 21				25 mg Days 1 - 21				25 mg Days 1 - 21			
Control Arm (Ld Arm)												
Cycle #	1 - 2				3 - 18				19 +			
Day # (-1/+3 days)	1	8	15	22	1	8	15	22	1	8	15	22
Dexamethasone - PO	40 mg	40 mg	40 mg	40 mg	40 mg	40 mg	40 mg	40 mg	40 mg	40 mg	40 mg	40 mg
Lenalidomide - PO	25 mg Days 1 - 21				25 mg Days 1 - 21				25 mg Days 1 - 21			

^a For elotuzumab and dexamethasone dosing, a window -1 to +3 days is permitted. In Cycles 3 and beyond, elotuzumab dosing may be delayed for up to 1 week as clinically indicated.

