4.5.3 Dose Delay or Interruption

If the dose of one drug in the regimen (ie, lenalidomide, dexamethasone or elotuzumab) is delayed or interrupted, the treatment with the other drugs may continue as scheduled. Subjects experiencing a 28-day delay in all study drugs lenalidomide, dexamethasone, and elotuzumab due to an adverse event(s) related to study treatment must be discontinued from study drug. Subjects experiencing delays unrelated to study therapy, for example due to radiation therapy may delay study treatment up to 42 days. Delays greater than 28 days must be discussed with the medical monitor.

Each cycle is 28 days. While dose delays or interruptions are permitted, the start of each cycle cannot be delayed and is fixed relative to Cycle 1 Day 1. Adjustments to the Cycle 1 Day 1 anchored schedule should not be performed. Missed doses should be skipped, not delayed, if not given within the allowed window.

Subjects may continue on study therapy even if components of the study therapy must be discontinued. For example, a subject on lenalidomide and dexamethasone may continue on study therapy even if dexamethasone must be discontinued for an adverse event. Likewise, a subject on

the investigational arm may continue on study therapy if elotuzumab must be discontinued for an adverse event or other reason. Patients are considered still on study therapy even if they continue solely on lenalidomide.

Please consult the BMS medical monitor or any questions regarding dose interruption or study therapy discontinuation.

4.5.3.1 *Elotuzumab*

In Cycle 1 and 2, an elotuzumab dose that falls outside of the pre-specified window (-1 to +3 days) must be skipped.

In Cycles 3 and beyond, elotuzumab dosing may be delayed for up to 1 week. If unable to administer within 1 week, then the dose should be skipped and resumption of the elotuzumab continues per the protocol defined schedule.

4.5.3.2 *Dexamethasone*

Dexamethasone delay should be performed as clinically indicated at the discretion of the investigator.

For subjects receiving elotuzumab, the weekly dexamethasone dose that coincides with or is temporally closest to the elotuzumab dosing must be administered as part of the premedication for elotuzumab per the guidance in [Section 4.5.1](#).

4.5.3.3 *Lenalidomide*

Lenalidomide delay should be performed as clinically indicated at the discretion of the investigator.

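### The SAP computes elotuzumab delays and omissions from the gap since the previous infusion, but the protocol ties each dose to the Cycle 1 Day 1 calendar, so some computed counts will be wrong

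*SAP*

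**What the plan says.** **Protocol.** Section 4.5.3 says that "the start of each cycle cannot be delayed and is fixed relative to Cycle 1 Day 1", and adds: "Missed doses should be skipped, not delayed, if not given within the allowed window". In Cycles 1 and 2, "an elotuzumab dose that falls outside of the pre-specified window (-1 to +3 days) must be skipped". Later the tolerance is wider: "In Cycles 3 and beyond, elotuzumab dosing may be delayed for up to 1 week". A dose is therefore on time, late or skipped relative to a planned day.

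**SAP.** Section 7.4.1.2 does not refer to the planned day. Its delay rule uses "the number of days from the start date of the previous infusion to the start date of the current infusion". The bands are:
- more than 8 and up to 10 days for Cycles 1 and 2 and the first infusion of Cycle 3;
- more than 15 and up to 21 days from the second infusion of Cycle 3 to Cycle 19;
- more than 29 and up to 35 days from Cycle 20.

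The omission rule uses the same interval. Its first cut-off is more than "10 days (in cycles 1, 2 or first infusion of cycle 3". The others are more than 21 days (to Cycle 18) and more than 35 days (from Cycle 19).

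Delays are grouped as 2-3 and 4-7 days. Omissions are summarised by gap length and by number per subject (1, 2, 3, or 4 and more). By-subject listings also show every CRF-reported delay and omission, whether or not it was computed.

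**The concern.** The gap between two infusions depends on the timing of both. If the previous dose was late, the gap shrinks and can hide lateness or a skip in the current dose. If it was early, the gap grows and can turn permitted dosing into an omission. A gap also cannot show how many planned doses fell inside it. The SAP's limits further assume one nominal interval and one tolerance per phase, and this fails where the phases meet, at Cycle 3 Day 1 and Cycle 19 Day 1. At stake is whether the computed delay and omission counts for elotuzumab describe what was delivered.

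**Working it through.** **Inputs.** Planned days and permitted offsets come from protocol 4.5.1 and 4.5.3: -1 to +3 days in Cycles 1-2, up to +7 from Cycle 3. Bands and cut-offs come from SAP 7.4.1.2. The band is taken from the cycle of the current (later) infusion. Only that reading explains why the first infusion of Cycle 3 sits in the weekly band.

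**Reproducing the SAP limits.** Nominal interval plus permitted lateness, with the previous dose on its planned day:
- weekly: 7 + 3 = 10
- two-weekly: 14 + 7 = 21
- four-weekly: 28 + 7 = 35

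All three match. Cycle 3 Day 1 is the exception: the interval is 7 and the permitted lateness 7, giving 14, but the SAP applies 10.

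**Formula.** Gap = planned interval + current offset - previous offset.

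| Case | Dosing | Gap (days) | SAP result | Against the planned day |
|---|---|---|---|---|
| a | C2D22 on time, C3D1 4 to 7 days late | 7+4-0 = 11 to 7+7-0 = 14 | omission | given, 4-7 days late |
| b | C18D1 on time, C18D15 skipped, C19D1 on time | 28+0-0 = 28 | neither (delay is 16-21, omission is >35) | one omission |
| c | Cycles 3-18: Day 1 at +7, Day 15 skipped, next Day 1 on time | 28+0-7 = 21 | delay | one omission; current dose on time |
| d | Cycles 3-18: two consecutive doses each at +7 | 14+7-7 = 14 | second dose: nothing | second dose 7 days late |
| e | Cycles 1-2: three weekly doses skipped, next on time | 4×7 = 28 | one omission | three omissions |

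**Sustained lateness.** Cycles 3-18 contain 16 × 2 = 32 doses. Suppose all are 5 days late after an on-time C2D22. The first gap is 7+5-0 = 12, an omission. The other 31 gaps are 14, which count as nothing. The SAP rule gives 0 delays and 1 omission; the calendar gives 32 late doses and 0 omissions.

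**Window edges in Cycles 1-2.** A dose at -1 followed by one at +3 gives 7+3+1 = 11, an omission with nothing skipped. A dose at +3, a skip, then a dose at -1 gives 14-1-3 = 10, a delay although one dose was skipped. Each is 1 of the 5 × 5 = 25 possible offset pairs.

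**Cases that depend on the early window.** From Cycle 3, -1 followed by +7 gives 14+7+1 = 22; from Cycle 20 it gives 28+7+1 = 36. Both count as omissions with nothing skipped. Both need the -1 day to apply after Cycle 2. The footnote to Table 4.5.1-1 says "For elotuzumab and dexamethasone dosing, a window -1 to +3 days is permitted" without naming cycles, whereas the text of 4.5.1 says "A window of -1 to +3 days is permitted in Cycles 1 and 2". If the early day applies only to Cycles 1 and 2, these two cases drop out; cases a to e and sustained lateness remain.

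**The case against.** The limits were not arbitrary: each equals the nominal interval plus permitted lateness, and away from the phase boundaries they classify a single late dose correctly when its predecessor was on its planned day. The Cycles 1-2 examples need opposite window extremes. The listings of CRF-reported events show that the SAP expects computed and reported events to differ, and protocol 4.5.1 requires the reason for a delay from Cycle 3 to be recorded. A 28-day gap in the weekly phase appears in the 28-35 day row, so its length is visible. The delay frequency line speaks of reported delays, so those counts may come from the CRF.

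Much of this stands, and it keeps the point small. It does not repair the computed counts. The gap-length summary covers only computed omissions, so cases b, c and d never reach it. The omission frequency line does not use the word reported. Reasons are summarised for subjects with an omission, so a false omission at Cycle 3 Day 1 may fall under *unknown*.

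A reader might infer that the trial would lose its record of elotuzumab delivery and tolerability. The documents do not support that. Cycles received, cumulative dose, dose intensity, infusion interruptions, discontinuations, adverse events and infusion reactions are all summarised separately. Nor do they support an inference that misclassification would be common: they give no distribution of visit timing, and equal counting of offset pairs is not an expected rate.

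**Conclusion.** The computed delay and omission rules are wrong as written, in both directions, under dosing and skipping that the protocol provides for. The clearest failures are at Cycle 3 Day 1 (a given dose counted as omitted) and Cycle 18 Day 15 (a skip counted as nothing). Neither needs an early dose or a late predecessor. Repeated lateness and consecutive skips are also undercounted.

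This is a minor point. It touches only descriptive elotuzumab exposure tables in the ELd arm. The ORR test, the PFS analyses and the sample size do not use these variables. The conclusion rests on the protocol windows as stated and on assigning each gap to the cycle of the later infusion. The frequency of misclassification is unknown.

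**What to change.** In SAP 7.4.1.2:
1. Compute each planned infusion day from the Cycle 1 Day 1 anchor. Planned days can be derived and need not already be stored.
2. For each dose given, report delay as actual minus planned day, including permitted lateness, in the existing 2-3 and 4-7 day categories.
3. Count as an omission every planned infusion, while the subject is still on elotuzumab, with no infusion inside its allowed window. State how the end of that period is determined, because a skip with no later infusion has no gap at all.
4. Make the two categories mutually exclusive.
5. Reconcile the limits for Cycle 3 Day 1 and Cycle 19 Day 1, and the early side of the window from Cycle 3, with protocol 4.5.1, Table 4.5.1-1 and 4.5.3. No dosing rule is proposed here.

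Delay should not be redefined as lateness beyond the permitted window. The protocol skips such doses, so that definition would capture only deviations, overlap with omission, and remove the permitted delays that the SAP sets out to tabulate.

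The cost is SAP wording and modest reprogramming. The listings of CRF-reported events can stay as they are.

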6.2 Treatment Regimens

Subjects will be randomized to one of two treatment arms, ELd or Ld. Subjects will receive these treatments in 28-day cycles until disease progression, unacceptable toxicity or withdrawal of consent.

On ELd arm subjects receive:

- Elotuzumab: 10mg/kg intravenous (IV) on Days 1, 8, 15 and 22 of the cycle during Cycles 1 and 2; Days 1 and 15 during Cycles 3-18 and 20mg/kg intravenous (IV) on Day 1 of the cycle during subsequent cycles.
- Lenalidomide: 25mg orally (po) on Days 1-21 of each cycle.
- Dexamethasone: Administered on Days 1, 8, 15 and 22 of cycle. 28mg po + 8mg IV whenever given prior to elotuzumab; 40mg po on weeks on which no elotuzumab is given.

On Ld arm subjects receive:

- Lenalidomide: 25mg po on Days 1-21 of each cycle.
- Dexamethasone: 40mg po on Days 1, 8, 15 and 22 of each cycle.

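### SAP 7.4.1.2 applies the Cycle 1-2 interval limit to the first infusion of Cycle 3, so some delays that the protocol permits there are counted as omitted doses

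*SAP*

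**What the plan says.** **SAP 7.4.1.2 (Dose Modifications, Elotuzumab)** classifies infusions by the interval between successive dosing dates.

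- Delay: "> 8 days and ≤ 10 days (if in cycles 1, 2 or first infusion of cycle 3"; wider bands apply later in treatment.
- Omission: "If the interval between the two dosing dates for Elotuzumab is >10 days (in cycles 1, 2 or first infusion of cycle 3"; the next limit is ">21 days (from the second infusion of cycles 3-18".
- Length of delay: "the time of delay in infusion will be summarized in the categories: 2- 3 days, 4 - 7 days".

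The first infusion of Cycle 3 is therefore grouped with Cycles 1 and 2 in both definitions.

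**The protocol** draws its line between Cycle 2 and Cycle 3. For the first two cycles, Section 4.5.3.1 says: "In Cycle 1 and 2, an elotuzumab dose that falls outside of the pre-specified window (-1 to +3 days) must be skipped". After that, Section 4.5.1 says: "In Cycles 3 and beyond, elotuzumab dosing may be delayed for up to 1 week as clinically indicated". The footnote to Table 4.5.1-1 repeats the allowance, and so does Section 4.5.3.1: "In Cycles 3 and beyond, elotuzumab dosing may be delayed for up to 1 week". Sections 4.5.1 and 4.5.3.1 have the dose skipped only if it cannot be given within that week. None of these places makes an exception for Cycle 3 Day 1.

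**The concern.** The SAP's other limits follow the protocol's windows, so a reader will take its omission table as a count of doses not given and its delay table as a count of doses given late. At the first infusion of Cycle 3 this fails. A dose that was given, within the lateness the protocol permits, can be tabulated as omitted. The 4-7 day delay category cannot be filled for this infusion at all, because the SAP's delay band there stops at 10 days, which is 3 days late.

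What is at stake is the accuracy of the exposure summary: omissions are overstated, delays are understated, and the reason for a late dose is sought in the omission table.

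**Working it through.** **Inputs**

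- Elotuzumab is given at "10mg/kg intravenous (IV) on Days 1, 8, 15 and 22 of the cycle during Cycles 1 and 2" (SAP 6.2), then on Days 1 and 15 in Cycles 3-18 and on Day 1 from Cycle 19.
- A cycle is 28 days, and the calendar is fixed to Cycle 1 Day 1 (protocol 4.5.3).
- Permitted lateness is 3 days in Cycles 1-2 and 7 days from Cycle 3 (protocol 4.5.1 and 4.5.3.1).

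**Step 1: reproduce the SAP's limits.** Limit = planned interval + permitted lateness.

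- Weekly dosing: 7 + 3 = 10 days
- Every two weeks: 14 + 7 = 21 days
- Every four weeks: 28 + 7 = 35 days

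All three SAP limits come out exactly, so the SAP evidently means to mirror the protocol's windows.

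**Step 2: the interval into Cycle 3.** With Cycle 1 Day 1 as study day 1, Cycle 2 Day 22 is 28 + 22 = 50 and Cycle 3 Day 1 is 56 + 1 = 57. The planned gap is 57 - 50 = 7 days. By the same formula, the limit under the protocol's Cycle 3 allowance is 7 + 7 = 14 days. The SAP has 10, which is the right planned interval with the Cycle 1-2 allowance.

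**Step 3: apply the SAP rule.** Let d be the days late at Cycle 3 Day 1 (0 to 7, all permitted) and s the shift of Cycle 2 Day 22 within its window (-1 to +3). The gap is 7 + d - s.

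| Cycle 2 Day 22 given | Gap (days) | d classed as delayed | d classed as omitted |
|---|---|---|---|
| 1 day early | 8 + d | 1-2 | 3-7 |
| On planned day | 7 + d | 2-3 | 4-7 |
| 1 day late | 6 + d | 3-4 | 5-7 |
| 2 days late | 5 + d | 4-5 | 6-7 |
| 3 days late | 4 + d | 5-6 | 7 |

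At every permitted shift of Day 22, at least one permitted delay is classed as an omission. By contrast, if the preceding dose is on schedule, the same 4-7 days of lateness at the second infusion of Cycle 3 gives a gap of 18-21 days, which the SAP calls a delay.

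**Step 4: what the 10-day limit does correctly.** Suppose Cycle 2 Day 22 was skipped and Cycle 3 Day 1 was on time. The previous infusion is Cycle 2 Day 15, study day 28 + 15 = 43, and the gap is 57 - 43 = 14 days. The current rule reports an omission, which is right. If Day 15 moved within its own window (study days 42 to 46), the gap is 11 to 15 days. A gap of 11-14 days can therefore mean either a late Cycle 3 Day 1 or a skipped Cycle 2 Day 22, and no single cut-off on the interval separates the two.

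**The case against.** **The grouping has a purpose.** The interval that ends at the first infusion of Cycle 3 is where a skipped Cycle 2 Day 22 shows up, and Day 22 falls under the Cycle 1-2 skip rule. This stands, and it rules out simply replacing 10 by 14: a dose never given would move from the omission count to the delay count. It does not rescue the present rule, which makes the opposite error for late doses.

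**The protocol fixes the start of each cycle.** Section 4.5.3 does so, and the footnote to Table 4.5.1-1 gives a window of -1 to +3 days. But the same sentence in 4.5.3 says that dose delays are permitted, and the same footnote adds the one-week allowance from Cycle 3. Neither withdraws the allowance at Cycle 3 Day 1.

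**The listings show the truth.** The by-subject listings include every delay and omission reported on the CRF, whether or not one was computed, so a true delay stays visible. The summary counts and percentages are still computed from dates, and a listing does not correct them.

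**A reverse error.** A reader might infer that a truly skipped Cycle 3 Day 1 would be reported as a mere delay, since Day 15 (study day 71) comes 71 - 50 = 21 days after Cycle 2 Day 22. The text does not support this. The SAP measures between infusions actually given, so on a plain reading Day 15 is then the first infusion of Cycle 3, and 21 days exceeds 10: an omission, as it should be. The error would arise only if that infusion were programmed as the second of the cycle, which the SAP does not say.

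**Conclusion.** The concern holds in a narrow form. For the first infusion of Cycle 3, SAP 7.4.1.2 does not match protocol 4.5.1 and 4.5.3.1, and the two must be reconciled. With Cycle 2 Day 22 on its planned day, lateness of 4-7 days at Cycle 3 Day 1 is permitted by the protocol and counted by the SAP as an omission. If Day 22 was 1, 2 or 3 days late, the affected range shrinks to 5-7, 6-7 or 7 days; if it was 1 day early, the range widens to 3-7.

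The size is small. At most one infusion per ELd subject is affected, and only in the descriptive delay and omission tables. ORR and PFS do not use these categories; nor does dose intensity, which SAP 7.4.1.3 computes from doses and dates.

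A reader might want to state how far the percentage with any omission is inflated. The documents do not support a figure: they give no rate of late infusions at this visit. With 40 ELd subjects, one misclassified subject moves that percentage by 1/40 = 2.5 points, and only if the subject has no other omission, because each subject counts once. Nor is the 11-14 day omission category wrong as a whole, since it also holds single doses truly skipped in Cycles 1-2.

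**What to change.** Amend SAP 7.4.1.2 for the first infusion of Cycle 3 in one of two ways.

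1. **Measure lateness from the scheduled date**, which protocol 4.5.3 anchors to Cycle 1 Day 1. A late Cycle 3 Day 1 and a skipped Cycle 2 Day 22 are then told apart directly, and shifts of Day 22 no longer matter.
2. **Keep the interval method with a condition.** When the previous infusion was Cycle 2 Day 22, call a gap over 8 and up to 14 days a delay and a gap over 14 days an omission. When Cycle 2 Day 22 was not given, keep the present rule that over 10 days is an omission.

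The first is cleaner. The second leaves a small residue: with Day 22 given 1 day early and Cycle 3 Day 1 given 7 days late, the gap is 7 + 7 + 1 = 15 days and is still called an omission.

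In either case, a short statement that the first infusion of Cycle 3 means the first one actually given would confirm the plain reading.

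The cost is a few lines of SAP text and slightly more programming than a single cut-off, using dosing dates already collected. The protocol's dosing rules are not touched.
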